1. INTRODUCTION AND RATIONALE

INTRODUCTION AND RATIONALE:

Distal radius fractures are the second most common fractures in the elderly population and cause high health-care costs per patient, especially in elderly patients^{1,2}. As a result of the high incidence and high costs per patient, distal radius fractures account for a substantial part of total health care costs^{3,4}. In the coming decades this will further increase by a progressively aging population⁵.

The treatment of distal radius fractures can be either non-operative or operative. The non-operative treatment consists of closed reduction followed by casting. The most commonly used operative procedures are external fixation, K-wire stabilization and open reduction and internal fixation (ORIF). Especially ORIF has gained in popularity. In the last decade it has become the most popular method of surgical treatment⁶. There is no evidence however that supports the superiority of this operative treatment over non-operative treatment but still the number of these surgical procedures is increasing^{6,7}.

Distal radius fractures can be either extra- or intra-articular. Very few extra-articular fractures are treated surgically. Intra-articular fractures however are more likely to be treated surgically, because articular incongruity resulting from a fracture is believed to cause arthritis⁸. About half of the distal radius fractures are intra-articular^{9,10}.

Patients with an intra-articular distal radius fracture who are treated surgically can rehabilitate faster because of surgical stabilization of the fracture. However, patients who are treated surgically are more likely to suffer from complications. Also surgical treatment is expensive and the long-term outcome does not seem to differ with that of non-operative treatment in terms of patient reported outcome measurements^{11,12}.

Non-operative treatment by closed reduction and casting is safe, simple, inexpensive and non-invasive¹³. A disadvantage is that up till 60% of fractures redislocate. However, several studies suggest elderly patients who are treated non-operatively have satisfactory function of their wrist even despite of malunion and poor radiographic outcome^{14,15}. Another downside to non-operative treatment is that it requires a longer duration of immobilization.

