5. TREATMENT OF SUBJECTS

ALL GROUPS

Study procedures:

Patients with an intra-articular fracture (AO type C) who meet the above mentioned inclusion criteria are eligible for the study. The surgeon on duty or the emergency physician is responsible for this initial screening.

In each eligible patient the surgeon on duty or the emergency physician will initially attempt to reduce the fracture after which the patient receives a temporary below-elbow forearm cast. For this, participating hospitals may use their preferred technique. Also they may follow their local protocol for anesthetics.

Preferably, eligible patients will receive information about the study at the emergency department.

One week after trauma they will be seen at the outpatient clinic. They can sign an informed consent form if they agree to participate up to 3 weeks after trauma.

Upon obtaining informed consent, patients will be randomized into either the surgical intervention group (open reduction and internal fixation) or the control group (closed reduction and plaster immobilization). For both treatment arms, participating hospitals may use their preferred technique. Also they may follow their local protocol for anesthetics, duration of cast treatment and vitamine C prescription. These data will be collected to correct for during data analysis.

In order to avoid any imbalance between treatment groups, patients will be randomized in 2 strata using a block randomization. Two strata according to age: 65-75 and 75 and older.

At baseline characteristics will be collected such as sex, side, dominant hand, trauma mechanism and the frailty questionnaire (frailty score <1 week after trauma).

Post-treatment patients will be seen at the outpatient clinic according to the regular protocol. These visits are also used for the follow-up assessments. Data is collected at 1 week, 3 weeks, 6 weeks, 3 months, 6 months, and 12 months. After 6, 9 and 12 months depending on the treating physician's and/or patients' preference they can visit the hospital or can be visited at home.

The Patient-Rated Wrist Evaluation score (PRWE), the Disability of the Arm, Hand and Shoulder (DASH), Quality of life (EQ-5D) and Costs evaluation questionnaire) will be obtained online or by hardcopy at baseline, 6 weeks, 3 months, 6 months, 9 months and 12 months. .

DART - Surgery vs. Casting for Displaced Articular Radius Fractures in Elderly

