2. CONTROL GROUP

[figure not shown]
The conservatively treated patient group receives a permanent circular cast between 1 and 2 weeks after trauma. The total duration of cast treatment may vary between 4-6 weeks according to local protocol. Vitamin C 500mg may be prescribed to prevent complex regional pain syndrome (CRPS) according to local protocols. Patients are referred for physical therapy according to local protocol or at the discretion of their treating physician. Unless there is a strong clinical indication, it is not possible for patients in the conservative arm to crossover to the operative group during the period of cast treatment (worsening of radiographic fracture characteristics or pain complaints during cast treatment are not criteria for crossover).

Use of co-intervention (if applicable)

Not applicable

Escape medication (if applicable)

Not applicable

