6.3 Study procedures

For a detailed description of the treatment in both groups see above. For a schedule of follow-up visits see table 1. Study procedures additional to standard care are highlighted.

	T0: 0 weeks	T1: 1 week	T2: 3 weeks	T3: 6 weeks	T4: 3 months	T5: 6 months	T6: 9 months	T7: 12 months
PRWE-score	X			X	X	X	X	X
DASH	X			X	X	X	X	X
Frailty score		X						
PCS				X				
EQ-5D-score	X			X	X	X	X	X
Economic questionnaire				X	X	X	X	X
X-ray of wrist		X	X(bilateral)	X	X			
ROM				X	X	X		X
Grip strength				X	X	X		X

Table 1: Questionnaires at follow-up time points.

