Both a cost-effectiveness analysis in terms of the primary outcome (i.e. PRWE) and a cost-utility analysis (i.e. Quality Adjusted Life Years; QALYs) will be performed. For the cost-utility analysis, the patients’ health-related quality of life will be measured at baseline, 3, 6, 9, and 12-month follow-up using the EQ-5D-5L²¹. The patients’ EQ-5D-5L scores will be converted into utilities using a Dutch tariff. QALYs will subsequently be calculated using linear interpolation between time points, with higher QALY scores indicating more improvement in quality of life.

Statistical analyses

Economic evaluations will be performed in accordance with the intention-to-treat principle and missing data will be handled using multiple imputation²². Incremental Cost Effectiveness Ratios (ICERs) and Incremental Cost Utility Ratios (ICURs) will be calculated by dividing the differences in costs by those in effects/utilities. Analyses will be performed using linear multilevel analyses in order to account for the possible clustering of data²³. Bootstrapping techniques will be used to estimate uncertainty surrounding the cost-effectiveness estimates, while adjusting for potential confounders. Uncertainty will be shown in cost-effectiveness planes and cost-effectiveness acceptability curves. Sensitivity analyses will be performed to test the robustness of the results (e.g. per-protocol analysis)^{20,24}.

BUDGET IMPACT ANALYSIS (BIA)

General considerations

Within this project, we will perform a budget impact analysis that is in accordance with the most recent guidelines of “The National Health Care Institute”¹⁸.

Cost analysis

In the budget impact analysis, the size and characteristics of the people aged 65 or older that suffer from a distal radius fracture will be estimated using Dutch epidemiological data. The effectiveness of the treatments will be extrapolated using a simple Markov model based on the estimates obtained in the proposed study. Within these analyses, the societal, healthcare, and insurer perspective will be considered. Monetary valuations will differ between these perspectives and different implementation scenarios will be evaluated.

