9.3 Benefits and risks assessment, group relatedness

The treatment that study participant receive is a component of standard treatment of care. Prior research suggests there is no difference in long-term function between both treatment groups. Currently the choice of treatment is based on the preference of the surgeon, the complexity of the fracture and the national guideline for the treatment of radius fractures.

Post-operatively or after cast therapy patients will be seen after 1 week, 3 weeks, 6 weeks, 3 months, 6 months and 12 months. These visits are standard care for patients following a fracture. In all these visits patients will be asked about complaints or complications, which is also part of regular care.

At baseline and after 6 weeks, 3 months, 6 months, 9 months and 12 months patients will be asked to fill out 4 questionnaires mentioned earlier as the main study parameters.

These questionnaires can be filled out at home online or in the hospital prior to their visit and will take approximately 30 minutes for each of these 6 data collection moments.

In total study participants will spend 210 minutes to this study. This includes informed consent and the questionnaires.

The risks of this study are comparable to risks involved with standard treatment. This comprises the standard risk for undergoing a surgical procedure, including risks related to anesthesia, neurovascular damage and post-operative wound infection. The risks of closed reduction and plaster immobilization include stiffness, redislocation, malunion, loss of function and complex regional pain syndrome.

Possible complications will be treated according to standard protocol.

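### The QALY time points omit the 6-week EQ-5D that the trial collects, so an early utility difference between the arms can drop out of the cost-utility result

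*Protocol*

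**What the plan says.** Section 8 (Cost effectiveness analysis, Patient outcome analysis) states for the cost-utility analysis that "health-related quality of life will be measured at baseline, 3, 6, 9, and 12-month follow-up using the EQ-5D-5L". It continues: "QALYs will subsequently be calculated using linear interpolation between time points". Six weeks is not in the list.

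The rest of the protocol has a 6-week measurement:

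- Section 5 (Study procedures) names the EQ-5D among the questionnaires that "will be obtained online or by hardcopy at baseline, 6 weeks, 3 months, 6 months, 9 months and 12 months".
- Table 1 in section 6.3 marks the EQ-5D row at baseline, 6 weeks, and 3, 6, 9 and 12 months.
- Section 9.3 describes the same burden to patients: "At baseline and after 6 weeks, 3 months, 6 months, 9 months and 12 months patients will be asked to fill out 4 questionnaires".

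On the timing of recovery, section 1 says that patients "treated surgically can rehabilitate faster because of surgical stabilization of the fracture", that casting means longer immobilisation, and that patient-reported outcomes do not appear to differ in the long term. For the control group, section 5 says: "The total duration of cast treatment may vary between 4-6 weeks according to local protocol". For the surgical group it allows an additional cast for at most 2 weeks after the operation.

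**The concern.** A QALY is an area under a utility curve, so the choice of time points is part of its definition. The list in section 8 leaves only a straight line between baseline and 3 months. A utility gap that opens after baseline and closes by 3 months then contributes nothing, although the trial will have measured it.

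The protocol's rationale points to that interval as the place where the arms should differ. If little difference is expected at 12 months, the omitted area could be a large part of the total QALY difference. That difference is the denominator of the incremental cost-utility ratio. It also feeds the acceptability curves, and the budget impact model may inherit it through the trial's effectiveness estimates. If surgical patients do recover faster, the omission shrinks the benefit credited to surgery and moves the result towards casting.

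**Working it through.** The protocol gives no utility, utility difference or QALY figure, so there is nothing of its own to reproduce. The check compares the trapezoid area on the two schedules.

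**Inputs from the protocol**
- Section 8 schedule: 0, 0.25, 0.5, 0.75 and 1 year.
- Collected schedule (section 5 and Table 1): the same points plus 6 weeks, which is 6/52.18 = 0.115 year.
- Linear interpolation on both (section 8).

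**Assumptions**
- Between-arm utility gaps d6 at 6 weeks and d3 at 3 months.
- No gap at baseline, nor at 6, 9 and 12 months.

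**Formulas**
- Section 8 schedule: the 6-week value has weight 0, and d3 has weight (0.25 + 0.25)/2 = 0.25. QALY difference = 0.25 × d3.
- Collected schedule: d6 has weight 0.25/2 = 0.125, and d3 has weight (0.5 − 0.115)/2 = 0.1925. QALY difference = 0.125 × d6 + 0.1925 × d3.
- Missed area = 0.125 × d6 − 0.0575 × d3 = 0.125 × (d6 − 0.46 × d3).

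**Results (QALY per patient, assumed gaps)**

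| d6 | d3 | Without 6 weeks | With 6 weeks | Missed | Share missed |
|---|---|---|---|---|---|
| 0.05 | 0 | 0 | 0.00625 | 0.00625 | 100% |
| 0.10 | 0 | 0 | 0.0125 | 0.0125 | 100% |
| 0.15 | 0 | 0 | 0.01875 | 0.01875 | 100% |
| 0.05 | 0.03 | 0.0075 | 0.0120 | 0.0045 | 38% |
| 0.10 | 0.03 | 0.0075 | 0.0183 | 0.0108 | 59% |
| 0.15 | 0.03 | 0.0075 | 0.0245 | 0.0170 | 69% |
| 0.10 | 0.10 | 0.0250 | 0.0318 | 0.0068 | 21% |

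Nothing is missed only when d6 is 46% of d3. The gap would then be smaller at 6 weeks than at 3 months, the reverse of the pattern that section 1 describes.

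**Can the sign change?** Take d6 = +0.10 and a constant gap of −0.01 from 3 to 12 months.
- Section 8 schedule: 0.25 × (−0.01)/2 + 0.75 × (−0.01) = −0.00125 − 0.0075 = −0.00875.
- Collected schedule: 0.115 × 0.10/2 + 0.135 × (0.10 − 0.01)/2 − 0.0075 = 0.00575 + 0.00608 − 0.0075 = +0.0043.

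So a reversal is possible when later differences are small.

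**In money.** At an assumed EUR 20,000 to 80,000 per QALY, 0.0125 QALY is worth 0.0125 × 20,000 = EUR 250 to 0.0125 × 80,000 = EUR 1,000 per patient.

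**The case against.** Five points can be made for the protocol.

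1. **The list may only be incomplete.** Section 8 never says that the 6-week value is excluded. It also calls the cost questionnaires three-monthly, although Table 1 has one at 6 weeks, so both sentences may be generic text that was never aligned with the schedule. This is plausible. But section 8 is where the QALY inputs are defined, and the same correction is needed on either reading. While both versions stand, the schedule can be chosen after the data are seen.

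2. **The direction is inferred.** Section 1 also expects more complications after surgery. Patients can consent up to 3 weeks after trauma, and visits are timed from trauma. A patient operated on at 3 weeks with 2 further weeks of cast would be only about 1 week out of cast at the 6-week visit, when a control patient may already be out of cast. The 6-week gap could then be small. This stands as a limit on the direction and size of the bias. It is no reason to leave the measurement out, since an early gap in either direction belongs in the QALY.

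3. **The size rests on assumed gaps.** This is true, and losing the entire difference requires no gap at any point other than 6 weeks. With a remaining 3-month gap the loss is partial, 21% in the mildest case shown.

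4. **An early difference would be seen elsewhere.** The EQ-5D is a secondary outcome, to be modelled with time and a time-by-group interaction, and section 8 plans sensitivity analyses. The model does not enter the QALY, and no sensitivity analysis on time points is named. Multiple imputation and bootstrapping do not help either, because the gap lies in the definition.

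5. **The scope is secondary.** This is correct: the primary non-inferiority test on the PRWE is not touched.

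**Conclusion.** The concern holds. Section 8 conflicts with section 5 and Table 1. Followed as written, it gives the 6-week EQ-5D a weight of 0 where the collected schedule would give it 0.125 year. Over assumed 6-week gaps of 0.05 to 0.15 and 3-month gaps of 0 to 0.10, the cases shown miss about 0.0045 to 0.019 QALY per patient, or 21% to 100% of the difference.

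The mismatch and the weights are certain. The direction is conditional on the early advantage for surgery that section 1 leads one to expect, and the sizes depend on utilities the protocol does not supply. The effect is confined to the economic evaluation and possibly the budget impact model. It should be corrected, but it does not threaten the trial's main conclusion.

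**What to change.** In section 8 (Patient outcome analysis), change the list of EQ-5D-5L measurements to baseline, 6 weeks, and 3, 6, 9 and 12 months. State that QALYs are the area under the curve over all of these points for every patient, with missing 6-week values handled by the multiple imputation already planned. Make the change before outcome data are examined. The description of the cost questionnaires as three-monthly can be aligned with Table 1 in the same edit.

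The cost is a change of wording. The 6-week questionnaire is already scheduled, so no visit, questionnaire, patient or burden is added.

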9 ETHICAL CONSIDERATIONS

9.1 Regulation statement

This study will be conducted according to the principles of the Declaration of Helsinki version 64, October 2013 and in accordance with the Medical Research Involving Human Subjects Act (WMO) and other guidelines, regulations and Acts.

9.2 Recruitment and consent

Patients diagnosed with a displaced AO type C wrist fracture will be approached by the investigator and informed about this trial. Patients will have a period of reflection of 5 working days. If the patient decides to participate, written and oral informed consent will be obtained (see appendix).

9.3 Benefits and risks assessment, group relatedness

The treatment that study participant receive is a component of standard treatment of care. Prior research suggests there is no difference in long-term function between both treatment groups. Currently the choice of treatment is based on the preference of the surgeon, the complexity of the fracture and the national guideline for the treatment of radius fractures.

Post-operatively or after cast therapy patients will be seen after 1 week, 3 weeks, 6 weeks, 3 months, 6 months and 12 months. These visits are standard care for patients following a fracture. In all these visits patients will be asked about complaints or complications, which is also part of regular care.

At baseline and after 6 weeks, 3 months, 6 months, 9 months and 12 months patients will be asked to fill out 4 questionnaires mentioned earlier as the main study parameters.

These questionnaires can be filled out at home online or in the hospital prior to their visit and will take approximately 30 minutes for each of these 6 data collection moments.

In total study participants will spend 210 minutes to this study. This includes informed consent and the questionnaires.

The risks of this study are comparable to risks involved with standard treatment. This comprises the standard risk for undergoing a surgical procedure, including risks related to anesthesia, neurovascular damage and post-operative wound infection. The risks of closed reduction and plaster immobilization include stiffness, redislocation, malunion, loss of function and complex regional pain syndrome.

Possible complications will be treated according to standard protocol.

9.4 Compensation for injury

The sponsor/investigator has a liability insurance which is in accordance with article 7, subsection 6 of the WMO.

10 ADMINISTRATIVE ASPECTS, MONITORING AND PUBLICATION

10.1 Handling and storage of data and documents

Data will be stored in two separate files. One data set will contain coded patient information and a second set medical history linked to these codes. The key to the code will be safeguarded by the coordinating investigator. Data will be stored and kept for fifteen years according standard guidelines. Only parties with obtained authorization will be able to review research data.

10.2 Amendments

All amendments will be notified to the METC that gave a favorable opinion. Non-substantial amendments will not be notified to the accredited METC and the competent authority, but will be recorded and filed by the sponsor.

10.3 Annual progress report

The sponsor/investigator will submit a summary of the progress of the trial to the accredited METC once a year. Information will be provided on the date of inclusion of the first subject, numbers of subjects included and numbers of subjects that have completed the trial, serious adverse events/ serious adverse reactions, other problems, and amendments.

10.4 End of study report

The investigator will notify the accredited METC of the end of the study within a period of 8 weeks. The end of the study is defined as the last patient's last visit. In case the study is ended prematurely, the investigator will notify the accredited METC, including the reasons for the premature termination.

Within one year after the end of the study, the investigator/sponsor will submit a final study report with the results of the study, including any publications/abstracts of the study, to the accredited METC.

10.5 Public disclosure and publication policy

The principal investigator is author, the study designer will be named author and the study coordinator will be named author. There will be a limit of ten authors. All others will obtain group authorship in the study group. All authors including group members are allowed to present the results.

12. APPENDIX
